## 7. ETHICAL ISSUES

Screening is by definition targeting people free of the target condition, and the benefit per participant is nearly always small. Consequently, any risk must also be small to justify the intervention. The primary screening tests are based on biochemical analyses of a blood sample, with minimal risks. All the other procedures in the trial (diagnosis and treatment among screen-positive men) are conducted in accordance with the normal standards of care and pose therefore no ethical issues. The study protocol will be submitted for review by the ethical committees of the Uusimaa and Pirkanmaa hospital districts. Permission for cancer registry linkage will be obtained from the National Institute for Health and Welfare (THL). Written informed consent is obtained from all screening participants for both the intervention and collection of data from electronic health records and health care registers for the analyses of the trial (cancer registry, cause of death registry, hospital discharge registry, regional laboratory and national prescription databases). Information about screening covers probabilities of abnormal screening test result, prostate cancer detection at biopsy given screen-positive result, frequency of biopsy complications, treatment options with their adverse effects, overdiagnosis in screening, as well as mortality impact of screening. The information is provided as a decision aid with graphically presented numerical results, modified from the earlier Finnish screening trial. A trial website will also be constructed to provide information on the progress of the study for the participants. According to the Finnish regulation, no consent is required for non-compliers or men in the control arm, but register data can be collected with permission from THL after an ethics committee review.

The trial can be stopped early for benefit or harm, if evidence for difference between the arms is obtained. For assessment of harm from the intervention, biopsy and treatment complications will be analysed, as well as incidence of advanced cancer (as an indicator of cancers missed by screening) and Gleason <7 cancer (as indicator of overdiagnosis) by arm are performed annually for the data monitoring committee. Monitoring of the main end-point (prostate cancer mortality) is carried out by an external committee. Interim analyses

are performed at five and eight years in accordance with sequential analysis rules (total alpha spending 0.005 of the two interim analyses according O'Brien-Fleming).

The study question satisfies equipoise criteria, i.e. balance of uncertainty (superiority of the evaluated intervention versus standard practice is not established). All procedures applied represent viable clinical options meeting current standards of care. The two screening tests based on a blood sample constitute the only experimental procedure performed solely for research purposes. Hence, the allocation based on randomisation is the only deviation from the normal health care and patient management. Screen-positive men are referred to diagnostic examinations just as any other patients, and undergo the procedures similar to other patients. This means that the results are readily applicable to public health policy. The generalisability is further enhanced by the Zelen-type randomisation, with consent sought only from the men in the intervention arm after randomisation. This ensures ethical conduct of research, as nobody is denied access to proper health care by the randomisation.

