Based on the FinRSPC first round results, we expect that the proportion of men with  $PSA \geq 3$  is 13% overall (10% in men aged 53-57, 17% for ages 58-62 and 24% at ages 63-65), total expected  $N=1452$ . This would mean on average 75 kallikrein panel determinations per month.

Screening interval is based on the initial PSA: men with  $PSA \geq 3$  are re-invited after two years, those with  $PSA > 1.5$  after four years, and the men in the lowest risk group ( $PSA < 1.5$ ) after six years.

After serum PSA as the initial test, we will use a four-kallikrein panel (4Kscore) to identify men at an increased risk of a clinically relevant prostate cancer. The determinations will be performed by prof. [name] in his lab in Malmö, with samples shipped every two weeks. These men will be referred to MRI and only MRI-positive men will be biopsied (randomised to targeted biopsy alone versus targeted and systematic biopsy).

The men with the highest risk of Gleason 7+ prostate cancer based on the kallikrein panel (out of those with  $PSA > 3$ ) will be regarded as screen-positive and referred to diagnostic examination at Tampere or Helsinki University Hospital urology clinic. The expected frequency is 871 men in the first round (60% of men with  $PSA \geq 3$ , or 7.8% of all participants), on average 45 men referred to MRI each month. This is substantially lower than in the PSA-based ERSPC trial (where on average 13% of the participants were screening-positive and referred to biopsy in the first round).

[figure not shown]

Figure 2. A CONSORT diagram illustrating the trial protocol and the expected distribution of men by test results

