#### Diagnostic procedures

The screen-positive men will undergo a multiparametric MRI using 3T equipment (Siemens Achieva) with 32-channel pelvic phased-array coil. T2-weighted, diffusion-weighted and dynamic contrast-enhanced imaging is employed in accordance with the European Society for Urogenital Radiology guideline. The findings will be classified according to the Prostate Imaging Reporting and Data System (PIRADS-2), which is a 5-point scale to combine the MRI findings and indicate the likelihood of a significant cancer (Osses 2017). A score of 4-5 indicates a PPV > 80% and also a score of 3 is regarded as a positive finding warranting biopsy. Standardisation of MRI procedures is ensured prior to the start of the trial, including slice orientation and thickness, and size of the matrix and field of view. Training sessions will be repeated annually throughout the conduct of the trial. Independent double reading for a random sample of the images is used for quality assurance, and to reduce false negative and false positive findings. Standardised and structured radiologists' reports will be obtained and prostate volume also recorded. Pseudoanonymised images are uploaded into the cloud-based trial database using the ECRF software tailored for the trial purposes.

The men with positive MRI will undergo targeted biopsy using fusion MRI-TRUS guidance (UroNav), with an additional core per each incremental 6 mm size of the lesion. The expected frequency of positive MRI is 60% of screen-positive men (4.7% of all screening participants), with a total of 521 men in the first round. To avoid missing cancers among high-risk men, those with PSA density (serum PSA divided by prostate volume) > 0.15  $\mu\text{g}/\text{ml}^2$  will be referred to systematic biopsy despite a negative MRI (Distler 2017). A random sample of those men with PSA  $\geq 3$  but (1) negative kallikrein panel and/or (2) negative MRI will also undergo systematic biopsy for assessment of diagnostic accuracy. A small number of men will not be eligible for MRI due to metal implants, and for them transrectal ultrasound (TRUS) will be used instead.

The prostate biopsies are evaluated by trained, experienced uropathologists under supervision of [name] in Helsinki and [name] in Tampere. Structured and standardised reports are used, with each core is evaluated separately and exact location recorded. Training and standardisation will be conducted

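### Section 7 calls the two blood tests the only research-only procedure, but section 4 orders biopsies for diagnostic accuracy in men with a negative kallikrein panel or MRI

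*Combined protocol and SAP*

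**What the plan says.** Section 7 makes three linked statements.

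- On research procedures: "The two screening tests based on a blood sample constitute the only experimental procedure performed solely for research purposes".
- On departures from usual care: "the allocation based on randomisation is the only deviation from the normal health care and patient management".
- On everything other than the blood tests: "All the other procedures in the trial (diagnosis and treatment among screen-positive men) are conducted in accordance with the normal standards of care", from which it concludes that no ethical issue arises.

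Section 4 describes more than that. Under Screening protocol, the general rule is that "only MRI-positive men will be biopsied (randomised to targeted biopsy alone versus targeted and systematic biopsy". Under Diagnostic procedures there are two exceptions, each with its own reason. The first is clinical: "To avoid missing cancers among high-risk men, those with PSA density (serum PSA divided by prostate volume" above a threshold are biopsied despite a negative MRI. The second is a random sample of men with PSA of 3 or more whose kallikrein panel and/or MRI was negative; men with a negative panel and/or "negative MRI will also undergo systematic biopsy for assessment of diagnostic accuracy".

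On information to participants, section 7 lists among other items "prostate cancer detection at biopsy given screen-positive result" and how often biopsy complications occur. On harms, section 4 (Data collection) gathers biopsy complications by questionnaire at four weeks, with hospitalisation and prescription data. Section 7 provides for analysis of biopsy complications and annual reporting to the data monitoring committee.

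**The concern.** The second exception is an invasive procedure. Men are chosen for it by chance, outside the stated pathway, and the plan gives no reason for it except measuring test accuracy. That makes it a research procedure, yet section 7 says there is none beyond two blood tests.

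Three things depend on this. First, section 7 argues that benefit per screened man is small and so risk must be small too; an ethics committee weighing that from section 7 alone would not learn of these biopsies. Second, the listed information describes biopsy after a screen-positive result and does not mention selection for biopsy after a negative panel or MRI. Third, the trial asks whether a three-step algorithm reduces harm. Complications and low-grade cancers arising from accuracy-sample biopsies are not produced by that algorithm, and they can occur only in the screening arm.

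**Working it through.** **Reproducing the plan's first-round cascade** (sections 3 and 4)

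- Screening arm: 67,000 / 4 = 16,750.
- Participants: 16,750 × 2/3 = 11,167 (stated 11,167).
- PSA of 3 or more: 0.13 × 11,167 = 1,452 (stated 1,452).
- Kallikrein-positive: 0.60 × 1,452 = 871 (stated 871).
- MRI-positive: 0.60 × 871 = 523 (stated 521, a trivial difference; 521 is used below).

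**Size of the sampled pool**

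- Kallikrein-negative: 1,452 − 871 = 581.
- Kallikrein-positive, MRI-negative: 871 − 521 = 350.
- Together: 581 + 350 = 931, and 931 / 1,452 = 64%.

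This is an upper bound, because some of the 350 are biopsied under the PSA-density rule and the plan does not say how many.

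**Number of accuracy-sample biopsies.** The plan gives no sampling fraction. The fractions here are assumptions. The share is of these biopsies plus the 521 MRI-positive men, with PSA-density biopsies left out:

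- 5%: 0.05 × 931 = 47; 47 / (47 + 521) = 8%.
- 10%: 0.10 × 931 = 93; 93 / (93 + 521) = 15%.
- 20%: 0.20 × 931 = 186; 186 / (186 + 521) = 26%.

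**Effect on the overdiagnosis indicator.** The plan expects 290 screen-detected cases, 75–80% of them Gleason 7 or higher. That leaves 20–25%, or 58 to 73, below Gleason 7. If 10–20% of 93 accuracy-sample biopsies found Gleason <7 disease (both the 93 and the yield are assumptions), that would add about 9 to 19 cases to the screening arm.

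**Setting the text side by side**

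- *Research-only procedures.* Section 7 allows two blood tests. Section 4 adds a biopsy with an accuracy purpose and no other. The PSA-density rule, listed separately with a clinical reason, shows that the plan itself distinguishes the two purposes.
- *Screen-positive men.* Screening protocol defines these as the men at highest risk on the kallikrein panel. The 581 kallikrein-negative men are therefore outside section 7's description of the other procedures. The 350 MRI-negative men are inside it, but biopsy of a random few of them is still outside the rule that only MRI-positive men are biopsied.
- *Only deviation from normal care.* If this is the allocation to arms, it does not cover a second random selection for biopsy within the screening arm.

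**The case against.** The best defence is that systematic biopsy at raised PSA is an accepted clinical procedure, and section 7 says all procedures used are viable clinical options. The plan also notes that in the earlier PSA-based European trial, screen-positive men were referred straight to biopsy. This shows that the technique is in clinical use. It does not make a biopsy clinically indicated when the man is picked at random to estimate accuracy, so the contradiction remains.

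Other objections do stand, and they rule out some stronger readings.

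- A reader might infer that harms from these biopsies will go unmonitored, or be pooled so that the committee cannot see them. The documents do not support that. Biopsy complications are collected and reported; the layout of the report is simply not specified.
- A reader might infer that men are not told. That cannot be judged. The section 7 list is a summary, it includes biopsy complications in general, and the consent pages were not available for review.
- A reader might treat all 931 men as outside section 7's screen-positive description. Only the 581 are.
- A reader might take 47, 93 or 186 as expected biopsy counts or as a measure of harm. They illustrate scale under assumed fractions, and no complication count can be derived from them.

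**Conclusion.** The contradiction between section 4 and section 7 is explicit and in current text. Section 7 claims a safety property that the design, as written, does not have. High confidence attaches to that textual conflict. The consequences for information and monitoring are gaps in specification, not demonstrated failures.

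The number of men affected is unknown. The upper bound of 931 assumes the plan's expected proportions and that every kallikrein-positive man has a usable MRI result. At the assumed fractions, accuracy-sample biopsies could be a visible minority of all biopsies, enough to matter when complications and Gleason <7 cases are credited to the algorithm. Prostate cancer mortality, its Cox analysis and its power calculation are untouched. The correction should be made, but the trial does not hinge on it. Nothing here takes a view on which men should be biopsied.

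**What to change.** 1. Reconcile sections 4 and 7. If the accuracy sample stays as written, name it in section 7 as a research-only invasive procedure, and amend the statements on the only research procedure, the only deviation from usual care, and standard care among screen-positive men.
2. Add to section 7's information list that a man may be selected for biopsy for research after a negative panel or negative MRI, unless the participant leaflet already says so.
3. In the annual harm report, tabulate complications by biopsy indication (pathway, including the PSA-density rule, versus accuracy sample). Attribute only the pathway complications to the screening algorithm.
4. Keep every case in the by-arm, intention-to-screen comparison of Gleason <7 incidence. Add a sensitivity analysis without cases found only by accuracy-sample biopsies, since these arise in one arm only. Some of those cancers might have surfaced later anyway, so this should supplement the main comparison and not replace it.

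The cost is some wording, one extra split in an annual report already planned, and one sensitivity analysis. Biopsy indication has to be recorded for each biopsy. The real downside is that some men may decline the accuracy biopsy once told of it, which would weaken the accuracy estimates.

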## 8. RISKS

The fundamental idea of the trial is the uncertainty about the effects of prostate cancer screening and the rationale rests on the assumption that the approaches, which have never been evaluated in a randomised trial and never combined into a single protocol, can be successfully integrated into a winning formula. However, a RCT has the advantage that even in a negative result is informative, i.e. proving that the proposed concept does not work, advances our understanding of the issue, here prostate cancer screening. The study is unique, and the closest counterparts either use PSA alone and lack one layer of risk stratification (Göteborg2 study) or have entirely failed to use randomisation (Sthlm3 study) and hence fall short of the scope of the present proposal.

Among the less fundamental issues, we expect a similar participation proportion as in the previous Finnish screening trial (67% at the initial round, and a similar level retained in the subsequent rounds).

The anticipated effect size, i.e. magnitude of mortality reduction achievable may be overstated. In the European screening trial (ERSPC), the relative reduction in prostate cancer has remained at 20% from 9 years to 13 years of follow-up (Schröder 2009, 2014). If the two risk stratification methods used for screening (kallikrein panel and MRI) both have 90% sensitivity for clinically relevant prostate cancer, a realistic effect size might be  $0.9 \times 0.9 \times 0.2 = 0.16$  i.e. 16% reduction. However, the shorter screening interval for men with PSA >3 is likely to compensate this at least partly. For instance, the majority of prostate cancer deaths up to 19 years of follow-up was among men with a baseline PSA >3 in the screening participants in the previous Finnish trial, suggesting that the shorter screening interval in such men is likely to enhance the screening effect.

Prostate cancer mortality has declined in Finland from 60 to 50 per 100,000 in 2002-2014, and the power calculations are based on the most recent mortality rates. If the decreasing trends continue (with further advances in treatment outcomes), the observed death rates could be lower by up to a quarter relative to those used in the power calculations. Assuming 469 prostate cancer deaths from prostate cancer at 15 years, instead of 581, would reduce the statistical power and allow us to detect a minimal difference of 31% (HR ≤ 0.69).

Active surveillance, with curative treatment postponed until signs of disease progression, has gained popularity in management of prostate cancer recently (Moschini 2017). Though treatment results of active surveillance have been highly favourable, it has a potential to decrease the screening impact as in some cases it may result in undertreatment and poor outcomes.

Statistical power can also be reduced by dilution of the contrast in the intervention between the arms. Spillover means intervention becoming available also to the control arm during the trial. PSA testing prior to baseline would also reduce the expected impact of screening. PSA testing frequency (including diagnostic assessment of men with urological complaints, as well as monitoring of men treated for prostate cancer, besides testing for screening purposes) was very high (up to >20%) in Finland after 2000 (Kilpeläinen 2017), but the stark reduction in prostate cancer incidence by a quarter in the past 10 years clearly suggest a decline its popularity.

Any future changes on clinical practice regarding diagnosis or management of prostate cancer will be incorporated in the protocol and applied to all men in the study. For instance, a faster, simpler MRI protocol (biparametric imaging) is being developed, and recent evidence indicates that adding abiraterone in the first-line endocrine treatment of metastatic prostate cancer may improve treatment results.

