### 3. TARGET POPULATION

We will identify all 67,000 men aged 50-63 years and residing in Tampere or Helsinki from the Population registry, and after exclusion of men with a prior diagnosis of prostate cancer (expected number 200), randomize them into two trial arms in ratio 1:3 (16,750 men allocated to the screening arm expected). Randomization is based on computer-generated random numbers and will be conducted in five batches annually (10% of the entire population at a time). This procedure is chosen in order to include only men alive and free of prostate cancer (with up-to-date information on cancer and vital status). Men with a permanent address abroad are not eligible.

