## 6. POWER CALCULATIONS & STATISTICAL ANALYSIS PLAN

The main outcome of the trial is prostate cancer mortality. An intention to screen analysis will be performed, with all men in the groups defined by random allocation, regardless of compliance. This is the gold standard for randomised trials, as it gives an unbiased effectiveness estimate, which is realistic for application (though lower and 'diluted' compared with an efficacy estimate based on compliers only). The only post-randomisation exclusions will be based on prostate cancer diagnosis prior to entry, as inevitably some recent cases will be found out only after randomisation. Follow-up starts at randomisation, and ends at death. Dates of death are registered also for men who have emigrated, but in case of a missing cause of death, the event will be censored. Cox regression will be used with prostate cancer death as the outcome. Randomisation is expected to result in balanced distribution of age, with no need for adjustment.

Based on the most recent age-specific population rates (2010-2014) and the age structure of the male population, the expected number of prostate cancer deaths in the control arm is 222 at 10 years, with sufficient statistical power ( $1-\beta=0.8$ ,  $\alpha=0.05$  two-sided) to detect a 33% reduction (hazard ratio,  $HR\leq 0.67$  for the screening arm, cumulative mortality 29 vs. 44 per 10,000 men) in prostate cancer mortality. This is calculated considering the overall mortality from other causes (ranging from 7 per 100,000 at age 55 to 210 per 100,000 at age 75), yielding a total of 475,000 person-years of follow-up. At 15 years of follow-up, the expected number of deaths in the control arm is 451, with a minimal detectable effect size of 26% ( $HR\leq 0.74$ , 67 vs. 90 deaths per 10,000 men, based 912,800 person-years of follow-up).

A secondary analysis of prostate cancer mortality will be performed using the Cuzick method to correct for non-compliance and contamination (Cuzick 1997, Roobol 2009, Kilpeläinen 2015).

Intermediate outcomes include cumulative incidence of advanced (T3-T4 or M1) prostate cancer (number of cases relative to population size, not using incidence density to avoid the lead-time bias due to early

detection by screening), and cumulative incidence of low-risk cancer (Gleason<7) as an indicator of overdiagnosis.

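### Section 8's 31% detectable reduction (HR 0.69) does not follow from its 469 deaths: at section 6's power and alpha, 469 deaths in both arms give about 26–29%

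*Combined protocol and SAP*

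**What the plan says.** Section 8 first notes that death rates could end up to a quarter below those used in the power calculations. It then puts figures on this: "Assuming 469 prostate cancer deaths from prostate cancer at 15 years, instead of 581, would reduce the statistical power and allow us to detect". The effect named there is "a minimal difference of 31" per cent, with HR 0.69 in brackets. It does not say whether 469 and 581 count one arm or both, and it gives no power, significance level or formula.

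The design settings are elsewhere. Section 6 sets 80% power and a two-sided 0.05 level, and names the analysis: "Cox regression will be used with prostate cancer death as the outcome". Section 3 gives the allocation: "randomize them into two trial arms in ratio 1:3 (16,750 men allocated to the screening arm expected"), which leaves 50,250 of the 67,000 men in the control arm.

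Section 6 has two benchmarks of its own, both labelled by arm. For 10 years, "the expected number of prostate cancer deaths in the control arm is 222 at 10 years, with sufficient statistical power" to detect a 33% reduction (HR 0.67). For 15 years, "At 15 years of follow-up, the expected number of deaths in the control arm is 451, with a minimal detectable effect size of 26" per cent (HR 0.74), with cumulative mortality of 67 against 90 per 10,000.

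**The concern.** The section 8 sentence varies one input, the number of deaths, from the 15-year calculation in section 6. Going from 581 to 469 deaths is a fall of 19% (469/581 = 0.807). The detectable log hazard ratio grows roughly with the inverse square root of the deaths, so it should rise by about 11%. The step from HR 0.74 to HR 0.69 raises it by about 23% (0.371/0.301), roughly twice as much.

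This is the document's only quantified statement of what the trial could still detect if mortality keeps falling. It stands shortly after a suggestion in the same section that 16% may be a realistic effect, so readers will compare the two. If 469 is right, 31% makes the design look weaker than it is. If 31% is right at 80% power, the death count is too high.

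**Working it through.** **Inputs.** Screening arm 16,750, control arm 50,250, so the screening share is 0.25 (section 3). Power 80% and two-sided 0.05 (section 6), so (1.960 + 0.842)² = 7.849. Deaths 469 and 581 (section 8); 222 and 451 control deaths (section 6). Carrying section 6's power and alpha into section 8 is an assumption, because section 8 states none.

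**Three readings of a death count D.** (a) Actual both-arm total: control deaths are 3D/(3 + HR), and the rest are in the screening arm. (b) Both-arm total expected with no screening effect: control deaths are 0.75D, and screening deaths are HR × 0.25D. (c) Control deaths only: screening deaths are HR × D/3.

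**Three formulas, each solved for HR.** Below, d1 and d0 are deaths, n1 and n0 are men and p1 and p0 are cumulative proportions, in the screening and control arms; p̄ is the pooled proportion.

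- Schoenfeld: (ln HR)² = 7.849 / [0.25 × 0.75 × (d1 + d0)]
- Log rate ratio: (ln HR)² = 7.849 × (1/d1 + 1/d0)
- Two proportions: p0 − p1 = 1.960 √[p̄(1 − p̄)(1/n1 + 1/n0)] + 0.842 √[p1(1 − p1)/n1 + p0(1 − p0)/n0]

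**Section 6's own figures first, then section 8's.**

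| Deaths and reading | Schoenfeld | Two proportions | Log rate ratio | Stated HR |
|---|---|---|---|---|
| 222 control (10 years) | 0.675 | 0.652 | 0.638 | 0.67 |
| 451 control (15 years) | 0.762 | 0.751 | 0.744 | 0.74 |
| 581, no-effect total | 0.758 | 0.747 | 0.7395 | none |
| 469, actual total | 0.742 | 0.729 | 0.721 | 0.69 |
| 469, no-effect total | 0.734 | 0.720 | 0.711 | 0.69 |
| 469 control | 0.766 | 0.755 | 0.749 | 0.69 |

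Section 6's figures come out approximately: Schoenfeld matches at 10 years and the log rate ratio at 15 years. Section 8's figure does not come out in any cell.

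Two cells by hand:

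- Schoenfeld, actual total of 469: ln HR = −√[7.849/(0.1875 × 469)] = −0.299, so HR 0.742 (25.8%).
- Log rate ratio, no-effect total of 469: d0 = 351.75 and d1 = 83.3, so ln HR = −√[7.849 × (1/83.3 + 1/351.75)] = −0.341 and HR 0.711 (28.9%).

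Freedman's formula, unpooled proportions and a continuity correction also fall within 25.8–28.9% for 469 both-arm deaths.

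**A check that needs no choice of formula.** Take section 6's 15-year HR of 0.74 as belonging to 581 deaths and scale it: exp[ln 0.74 × √(581/469)] = exp(−0.301 × 1.113) = 0.715, or 28.5%. If 0.74 is a rounded 0.735–0.745, the result is 27.9–29.0%. The pairing with 581 is mine. Section 6's rates imply 451 + 16,750 × 0.0067 = 563 actual deaths, or 451 × 4/3 = 601 with no effect. Scaling from those gives 0.719 and 0.711.

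**The reverse question.** Deaths needed for 80% power at HR 0.69, as an actual total:

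- Schoenfeld: 7.849/(0.1875 × 0.371²) = 304
- Two proportions: 350
- Log rate ratio: 375 (406 as a no-effect total)
- Scaling from 581: 581 × (ln 0.74/ln 0.69)² = 383

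If 0.69 is a rounded 0.695, the three formulas need 316, 362 and 388 (420 as a no-effect total by log rate ratio), all still below 469. With 469 deaths, power at HR 0.69 is 0.94, 0.91 and 0.88 (actual total) or 0.92, 0.88 and 0.85 (no-effect total), in the table's order of formulas.

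**The case against.** The strongest reply is that section 8 states no power, so a higher one may have been used. At 85% power, the log rate ratio with 469 as a no-effect total gives HR 0.691. At 90%, the both-arm readings give 0.667–0.708, which spans 0.69. This is possible, but neither level appears in the document. At 85% the same formula gives 0.726 for 451 control deaths and 0.614 for 222, against the stated 0.74 and 0.67. At 90% the formulas give 0.705–0.729 and 0.583–0.633. Section 8 would then be using a different, undisclosed standard from section 6.

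A second reply is that the scenario was meant to be a full one-quarter fall. That is 0.75 × 581 = 436 deaths and gives at most 30.0% (HR 0.700). It comes close, but it is neither 31% nor the stated count. Allowing for the interim alpha spending of 0.005 in section 7 (final level 0.045) gives 26.2–29.4% for 469 both-arm deaths.

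Two criticisms of the check stand. No formula tried reproduces both section 6 benchmarks: the log rate ratio, closest at 15 years, misses the 10-year HR by about 3 points. And 581 matches neither total implied by section 6 (563 or 601), so section 8 may come from a separate calculation. The planners' method is therefore unknown, and the replacement should be read as a range. Neither criticism rescues 31%, because the log rate ratio is already the formula most favourable to it and stops at 28.9%.

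It is also fair that the trial could detect 31% with 469 deaths, at 85–94% power. Only the claim that this is the minimum fails.

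**Conclusion.** The concern holds. Under section 6's power and alpha and section 3's allocation, 469 deaths give a minimal detectable reduction of about 26–29% (HR 0.711–0.742) if they cover both arms, and 23–25% (HR 0.749–0.766) if they are control deaths. The stated 31% lies outside both ranges, by about 2 to 5 percentage points on the both-arm readings. The conclusion rests on carrying section 6's settings into section 8. It does not depend on the choice among the standard formulas tried, or on rounding of the stated HRs. The document does not show whether the count, the percentage or an unstated power is at fault. If 469 is right, the error overstates the loss of power. Nothing in the sample size, the conduct or the primary analysis changes. Minor.

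**What to change.** In section 8, say whether 469 and 581 are control-arm or both-arm deaths, and whether they are expected with or without a screening effect. Restate the detectable reduction using the formula, alpha and power behind section 6, and name that formula in both places. If 469 is the both-arm total, the new figure should be about 26–29%. If the 31% came from another death count or another power, correct or state that input instead. While doing so, reconcile 581 with the 563 or 601 deaths implied by section 6, and the 19% fall from 581 to 469 with the fall of up to a quarter mentioned just before it. The cost is one recalculation and one reworded sentence, plus the formula's name in section 6.
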